14.1 Data handling and quality assurance

Before initiating the study, acceptance from the Danish Data Protection Agency will be sought. All health-related matters and sensitive personal data will be handled in accordance with the Danish “Act on Processing of Personal Data”. All health-related matters and sensitive personal data (blood test result etc.) will be depersonalized. All participants will be given a study number referring to their personal information, which will be stored securely and separately. Adequate blinding of all personal data during data processing and publication will be ensured. Data will be stored in coded form in 10 years after last participant has attended the last visit, where after the data will be fully anonymised.

14.2 Source data identification and verification

All clinical study information in the study will be recorded, handled, and stored in a way that allows accurate reporting, interpretation and verification. All questionnaire data will be collected electronically using the software system “*REDCap*” according to local standards for research projects in the capital region of Denmark. In addition, all sources will be registered in this database. Data generated and stored for specific equipment (e.g. DXA data stored in the database in relation to the software used for the DXA scanner), EMR data (blood and urine measurements, glucose- and lipid-lowering medicine) from *Sundhedsplatformen*, data from iPro®2 CGM using software from Medtronic (Northridge, CA, US) to download CGM measurements, data on use of carbohydrate meal plan from a diary and dietary data on total energy and nutrients based on calculations from the software system *Vitakost* where dietary recordings are entered will be added to the database in *REDCap* on an ongoing basis and at the end of study. Data is stored in coded form for 10 years. Hereafter, data will be fully anonymized.

14.3 Data reporting and protection

Data are owned by the investigators. The investigators are responsible for publishing the results. Positive and negative as well as inconclusive study results will be published by the investigators in international peer-reviewed journals, and all co-authors must comply with the Vancouver rules. The author order depends on the different authors’ contributions to the study. All information on study participants is protected according to law on processing of personal data and the law of health. None of the study-related blood samples or data will be stored or analysed in countries outside the EU.

14.4 Study files

The following documents will be present at SDCC before study initiation can take place:

- Ethical approval of the protocol and informed consent document
- Signed protocol page
- Blank copy of the approved informed consent document and any other documents to the patients
- CVs of principal investigator and co-investigators
- Signed delegation log

In addition, study specific SOPs, training logs, and case report forms will be prepared and training sessions will be conducted to ensure standardization in relation to measurements taken before initiating the study recruitment of study participants.

Copies of all these documents as well as supplemental information, such as the final protocol will be kept at SDCC in an access restricted electronic trial master file. This file will also contain patient accountability records (screening and inclusion logs), correspondence with co-investigators and authorities, protocol deviations, and biological samples records. The investigator will keep a list of the patients, identifying the names (with identification number), their respective code number and the date of start of the study. All source documentation (i.e. medical notes, lab reports, etc.) will also be available in folders in coded form. The document identifying the patients by name and personal security number (CPR-number) will be kept in a separate folder with limited access which will be fully anonymized after 10 years.

15 Ethics and regulations

15.1 Independent ethics committee and regulatory authority

The study protocol will be submitted for approval by the Ethics Committee of the Capital Region, Copenhagen and the study will be registered for approval of data storage at the Danish Data Protection Agency. After obtaining an approval from all authorities the study will be registered at clinical trials.gov and initiated. A report summarizing the results of the study will be sent to the Ethics Committee of the Capital Region after the study.

15.2 Ethical conduct of the study

The study will be conducted in accordance with the ethical principles in the Declaration of Helsinki and to the regulations for Good Clinical Practice (GCP) to the extent that this is relevant for a non-medical study. The study will deliver important new knowledge on the effects of different dietitian-led dietary interventions in patients with T1D in relation to glucose regulation and related metabolic parameters. In addition, the results from the study will give valuable information on patient self-care and adherence to their diabetes treatment through which the patients may experience reduced fluctuations in plasma glucose levels, including hypoglycaemia and increased diet-related quality of life. The findings from the study may have direct patient-related implications for future national guidelines and may potentially reduce their long-term diabetes-related complications. This non-medical study has no obvious ethical concerns for the participants and only minor risks in relation to participation (please see section 15.3). The anticipated benefits for the participants are high including improved glycaemic control in terms of reduced HbA1c and plasma glucose variability as well as an improvement of diet-related quality of life and self-care.

15.3 Risks related to participation

Overall, limited risks are expected with the current study. All equipment used in the studies meet the requirements for patient safety and has previously been used in research projects without problems. There is a small risk of hypoglycaemia at the study visits where participants must meet after an overnight fast of 8-10 hours for study measurements in a fasting state at three visits (V1, V5 and V6). In such cases the study investigator and study personnel will take appropriate action to protect participants.

Blood samples

Collection of data in the present study involves blood samples. A minor risk of slight pain during injection of the needle is present, and the sampling might leave a minor bruise at the place of injection. This will disappear within one to two days. Blood will be collected at four visits during the study period of 48 weeks corresponding to a total amount of 185 ml including 30 ml blood for a biobank for future research.

In addition, the participants have a very low risk of having a low plasma glucose level at visits where fasting measurements are performed (please see Table 1).

CGM

CGM will be used to measure the interstitial glucose at near continuous intervals to obtain a 24-hour glucose profile for a period of 6 days. The use of CGM involves insertion of a glucose sensor on the lower part of the abdomen (under the umbilicus) with an introducer needle to aid in the insertion of the sensor into the subcutaneous tissue. There is a minor risk of slight pain during injection of the needle. Also, a minor risk of skin irritation or infection due to either the sensor needle or the adhesive can occur.

DXA

DXA will be used for the assessment of body composition two times during the study. The scan is an x-ray examination, but the degree of radiation the participants will be exposed to during a scan is very limited with a radiation dose less than 0.001mSv. For comparison, the yearly background radiation in Denmark is 3 mSv, which accounts for daily radiation of 0.008 mSv. This corresponds to category 1 in accordance with the classification based on the guidelines from the International Commission on Radiation Protection (ICRP) and the European Commission. This category corresponds to a stochastic damage by radiation exposure of normal research participants in the order of 1:1 million or less. This risk is considered negligible. The scans will be conducted with an appropriate speed based on the body weight and sagittal diameter of the study participant. The scan is performed with the study participant lying on the back on an open scan couch while the arm of the scanner passes by. The scan takes approximately 15 minutes, and in case of a failure, only once extra scan will be performed. All fertile women will be asked to clearly state lack of pregnancy according to local requirements and procedures, and in case of statement the scan will not be conducted.

15.4 Insurance of the patients

Patients are covered under the Patient Insurance Act (Lov om klage- og erstatningsadgang inden for sundhedsvæsenet, lov nr. 1113 07/11/2011).

15.5 Protocol changes

Substantial amendments to this protocol may be implemented only after a favourable opinion of the Ethics Committee of the Capital Region, Copenhagen has been obtained. Amendments to the protocol are regarded as substantial if they have a significant impact on

- The safety, physical health and mental integrity of the participants
- The scientific value of the study
- The conduct or the management of the study

Any amendments to this protocol will be signed by the signatories included in section 2. If an event occurs related to the conduct of the study which may affect the safety of the participants, the study investigator may take appropriate measures to protect the participants against immediate hazards. The investigator will inform the Ethics Committee of the Capital Region, Copenhagen of the new events and the measures taken as soon as possible.

15.6 Protocol deviations

No systematic deviations from the protocol are allowed, and no protocol waivers will be given. All protocol deviations noted during the study will be recorded and evaluated by the study investigator.

16 Organisation

16.1 Study tasks

Research assistant and principle investigator:

- Recruitment of study participants: Identification, telephone calls, screening
- Study logistics including data collection and registration (e.g. no shows, new appointments)
- iPro®2 for 6 days at V1 and V5
- DXA scanning at V1 and V5
- Instruction on urine collections and dietary recording at V1 and V5

Principal investigator:

- Data management, analysis and statistics
- Writing of scientific papers based on the study

Project dieticians:

Group A with project dietitian A+B ([name] and [name]):

- Carrying out eight courses (8-hours course) in BCC with two dietitians including one hour for course preparation per participant ~ 205 hours

Group B with project dietitian B+C ([name] and [name]):

- Carrying out eight courses (4-hours course) in ABC-ACC with two dietitians including two individual follow-ups (2x45 min) with a dietitian and one-hour course preparation per participant ~ 257 hours

Group C with project dietitian C ([name]):

- Individual dietary counselling (1x60 min and 2x30 min) in control group (usual care) ~ 154 hours

Bio analyst:

- Preparation of urine sampling kits
- Handling of incoming urine samples for the research biobank and a biobank for future research
- Collection of blood samples
- Analysis of blood samples in the study and handling of blood samples for storage in a biobank for future research
- Analysis of urine samples for albumin, creatinine and food intake biomarkers

17 Publication

Positive as well as negative and inconclusive results of the study will be published in English in relevant peer-reviewed scientific journals as well as parallel Danish publications e.g. the journal for clinical dietitians, the Danish Diabetes Association's journal for health care professionals and member's journal and at the SDCC's website.

17.1 Authorship

[name] will be first and corresponding author, [name] second author, [name] second last author and [name] last author on the first publication. Co-authors include [name], [name] and [name].

18 Study time-frame

The active study period will begin with patient recruitment from August 2018 and expected to be finalized by October 2021.

19 Initiative and financing

PhD student and Head of Nutrition [name] has taken initiative to this study together with Professor and Head of Clinic [name] at SDCC and [name], NEXS, University of Copenhagen.

The study has been partly funded by the Novo Nordisk Foundation as part of the non-standard initiatives at SDCC in 2018-2020 to cover salary for dietitians. Salary for the PhD-student, operating expenses and equipment are partly covered internally by the clinic and the clinical research at SDCC. External funding has been granted by the Beckett Foundation (150,000 DKR) and the Axel Muusfeldts Foundation (300,000 DKR) for salary for a research assistant. If further external funding is obtained, the Ethics Committee of the Capital Region, Copenhagen will be notified. The study investigators, study personnel and study dietitians have no economic benefits before, during and after the study.

The requirements in Appendix 1 are fulfilled in accordance to the Ethics Committee of the Capital Region, Copenhagen "Retningslinjer for vederlag og/eller andre godter til forsøgspatienter". No economic compensation will be given to the study participants. Transportation to SDCC will be covered according to standard procedures for standard care at SDCC in patients eligible for transport.

20 References

3. Kliniske retningslinjer for behandling af voksne med Type 1 diabetes. Sundhedsstyrelsen (Danish Health & Medicines Authority), Copenhagen; 2010.
4. Rammeplan for diætbehandling af type 1 diabetes Foreningen af kliniske diætister (The association of clinical dietitians); 2011.

## Section 2: Introduction

### Background and Rationale (adapted from study protocol)

The total amount of carbohydrates consumed in a meal is a major predictor of the postprandial glucose response (3). Thus, monitoring dietary intake of carbohydrates is important to control postprandial glucose fluctuations in type 1 diabetes (T1D). A reduction in postprandial glucose excursions may in turn lead to clinical benefits such as attenuated glucose variability and improvements of glycated haemoglobin A1c (HbA1c), and potentially to a reduction in diabetes-related complications. Clinical guidelines in medical nutrition therapy recommend that people with T1D learn carbohydrate counting or similar experience-based methods to improve glycaemic control (3-6).

Two levels of carbohydrate counting have been defined with increasing complexity: A basic and an advanced level (7-8). In brief, basic carbohydrate counting (BCC) includes education in estimating total carbohydrate amounts, and improving consistency in the timing, type, amount, and distribution of carbohydrate-containing foods at meals. Advanced carbohydrate counting (ACC) includes education in how to adjust mealtime insulin dose. Ideally, people with T1D treated on multiple daily injections (MDI) therapy need to be able to manage both levels. This includes managing two calculation steps several times daily when using carbohydrate counting: (1) Correct estimation of the total carbohydrate content at each meal (equal to BCC), and (2) Correct estimation of mealtime insulin dose according to the carbohydrate amount consumed at each meal using a carbohydrate-to-insulin ratio, an insulin sensitivity factor, and the current and target plasma glucose (equal to ACC). Thus, good mathematical skills are highly essential. However, studies have found that people with T1D frequently assess their intake of carbohydrates inaccurately and this has been associated with a poorer HbA1c, and higher daily plasma glucose variability (9-12). In clinical guidelines and trials, the term 'carbohydrate counting' is often used synonymously with ACC, while the sole effect of BCC on glycaemic control is largely unknown. Systematic reviews and meta-analyses of randomised controlled trials (RCTs) have shown that ACC can reduce HbA1c by up to 7 mmol/mol in adults with poorly controlled T1D (13-15). Despite this, systematic educating and training in BCC and ACC is still not offered routinely for people with T1D on multiple daily injections (MDI) therapy in outpatient clinics in Denmark. This may be due to the lack of evidence as to which educational methods are the most effective for training people, and the lack of appropriate learning environments to promote behavioural change and availability of trained dietitians to facilitate the learning process. Additionally, the concept of ACC may not apply to all people with T1D on MDI therapy e.g., due to lack of motivation, low literacy, or numeracy skills.

## Objectives

The primary objective of the DIET-CARB study is to investigate the effectiveness of two different educational approaches for carbohydrate counting (BCC and ACC) and usual dietary care on change in HbA1c and glycaemic variability (assessed by mean amplitude of glycaemic excursions (MAGE)) in people with T1D.

Secondary objectives were to describe changes associated with the intervention on other clinically relevant metabolic changes (body weight, body composition, blood pressure and lipid profile), changes in skills related to numeracy and carbohydrate estimation accuracy as well as on psychosocial and behavioural outcomes at the end of the intervention period and after 6 months of follow-up to assess long-term maintenance.

### Hypotheses for the primary outcomes:

1. We hypothesize that ACC is superior compared with usual dietary care (the control group) in reducing HbA1c or MAGE from baseline to end-of-treatment at week 24 (from V1 to V2).

Superiority is claimed if:

- a. the 95% confidence interval for the estimated difference in change between the groups for HbA1c or MAGE, estimated using a baseline corrected linear mixed model, excludes 0 and the P-value is <0.05: and,
- b. the estimated difference in HbA1c or MAGE between the two groups is equal to/surpass the minimal important difference in favour of the ACC group.

2. We hypothesize that BCC is superior compared with usual dietary care (control group) in reducing HbA1c or MAGE from baseline to end-of-treatment at week 24 (from V1 to V2).

Superiority is claimed if:

- c. the 95% confidence interval for the estimated difference in change between the groups for HbA1c or MAGE, estimated using a baseline corrected linear mixed model, excludes 0 and the P-value is <0.05: and,
- d. the estimated difference in HbA1c or MAGE between the two groups is equal to/surpass the minimal important difference in favour of the BCC group.

3. We hypothesize that BCC is equivalent to ACC in reducing HbA1c or MAGE from baseline to end-of-treatment at week 24 (from V1 to V2).

Equivalence is claimed if:

- e. The 90% confidence interval for the estimated difference in change between the groups for HbA1c or MAGE does not surpass minimal important difference in a negative or positive direction (16).

Hypotheses for the secondary outcomes can be found in the study protocol and [clinicaltrials.gov](https://clinicaltrials.gov).

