13.2 Statistical methods

Intention-to-treat (ITT) analysis will be performed as the primary analysis on all primary and secondary outcomes after the last participant has participated in the last visit. Missing values will be handled with a last observation carried forward approach for ITT analysis. Per-protocol (PP) analysis will only be performed in case of sensitivity testing.

Parametric tests (general linear models) will be used to test differences in outcomes from baseline to follow-up. Heterogeneity in responsiveness to the interventions will be tested by dividing each intervention group into smaller groups based on data distribution (medians) or clinically meaningful cut-points. If model assumptions cannot be met even after logarithmic transformation, non-parametric tests will be used. Plots of residuals versus predicted values will be used to judge normality. Metabolic patterns will be tested with multivariate statistics. Adjustment for relevant confounders will be performed. Two-sided tests will be used. *P* values of <0.05 are considered significant. The statistical programs SPSS and SAS will be used for data analysis.

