13.3 Determination of sample size

Allowing for drop-outs (~20%) and subgroup analyses we plan to include a total of 231 patients in our study. This is based on sample size calculations which suggested that including 64 participants in each of the study groups would give us 80% power to detect a clinically meaningful difference in change in HbA1c of 3.5 mmol/mol between the BCC group versus the control group or the ABC-ACC group versus the control group with a 5% significance level using a two-sided test and an estimated standard deviation (SD) of 7 mmol/mol. This SD has previously been used for sample size calculations in ACC trials (28) and was similar to what we found in our evaluation of our BCC courses on mean changes and SD of HbA1c after 6 months in completers with T1D (n=185). MAGE has only been used as an outcome measure of glucose variability in a few randomized controlled dietary intervention studies of patients with diabetes (42, 43) showing differences in changes in MAGE up to 4.8 mmol/l (SD: 1.0) after a 12-week carbohydrate counting intervention (42). By including 77 participants in each study group we will have a power of 80% (alpha level of 0.05) in a two-sided test to detect a clinically meaningful difference in the change in MAGE during the intervention period (week 24) of ≥ 0.35 mmol/l (SD 0.7 mmol/l) between the study groups as presented in **Table 5**.

Table 5: Sample size calculations

Difference in HbA1c, mmol/mol (SD 7.0)	Difference in MAGE, mmol/l (SD 0.7)	Net total no of participants in the study (BCC group vs control or ABC-ACC group vs control)	No of participants given a dropout rate of 20%
2.0	0.20	582	698
3.0	0.30	261	315
3.5	0.35	192	230
4.0	0.40	150	180

14 Data management

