### Sample size

See study protocol.

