### Timing of final analyses

The results will be analysed when this statistical analysis plan has been uploaded at [clinicaltrials.gov](https://clinicaltrials.gov)

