## Section 4: Statistical Principles

### Confidence intervals and P values

Two-sided P-values and 95% confidence intervals will be presented for comparisons between groups. Two-sided 95% confidence intervals will be presented for within group comparisons and estimated levels.

**Primary outcome:** The direction and size of the estimated mean effect for HbA1c and MAGE (primary outcomes), in addition to the 95% confidence intervals, will be required to support the tested hypotheses for the results to be declared in accordance with the hypotheses (see section 2 under “Objectives”).

**Secondary outcomes:** False detection rate (FDR) correction ad modum Benjamini and Hochberg (17) will be used to control for multiplicity; < 5% will be used as the threshold for FDR.

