## Section 6: Analysis

### Outcome definitions

#### **Primary outcomes**

HbA1c and MAGE. The treatment effect will be given as the baseline corrected difference in mmol/mol for HbA1c and mmol/l for MAGE between the ACC versus the control group, and the BCC versus the control group at V2.

Estimation of minimal important difference for primary outcome: Reductions in HbA1c of 3.5 mmol/mol and 0.35 mmol/l of MAGE were defined as minimal important differences in this trial. This was based on findings from experimental studies examining the HbA1c effect of BCC (19-21), and meta-analyses of RCTs examining the HbA1c effect of ACC (13-14) vs. control or usual dietary treatment. In these studies, HbA1c reductions between 3 to 7 mmol/mol had been found in adults with T1D. All participants in the studies had a more poorly controlled diabetes (60-108 mmol/mol) than participants eligible for inclusion in our study (53-97 mmol/mol). Consequently, we expected to find smaller HbA1c reductions in our study population. This was considered clinically relevant as part of a multidisciplinary approach for improving glycaemic control in T1D.

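### The protocol's 80% power does not apply to the SAP's two-part superiority rule, which is met only 50% of the time at the planned effect

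*SAP*

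**What the plan says.** Protocol 13.3 says that "including 64 participants in each of the study groups would give us 80% power to detect a clinically meaningful difference" in HbA1c change of 3.5 mmol/mol for either active arm against control, "with a 5% significance level using a two-sided test and an estimated standard deviation (SD) of 7 mmol/mol". For MAGE it uses 0.35 mmol/l with SD 0.7 mmol/l, and Table 5 puts both differences on the same row, at 192 evaluable participants in three arms. The only success criterion in Protocol 13.2 is that P "values of <0.05 are considered significant".

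The SAP (Section 2, Hypotheses for the primary outcomes) sets a stricter rule with two conditions that must both hold. The 95% CI must exclude 0 with P<0.05, and "the estimated difference in HbA1c or MAGE between the two groups is equal to/surpass the minimal important difference in favour of the ACC group". Items c and d repeat this for BCC. Section 4 confirms that it is intended: "The direction and size of the estimated mean effect for HbA1c and MAGE (primary outcomes), in addition to the 95% confidence intervals" must support the hypothesis. Section 6 fixes the threshold: "Reductions in HbA1c of 3.5 mmol/mol and 0.35 mmol/l of MAGE were defined as minimal important differences in this trial". The whole of the SAP's sample size section reads "See study protocol".

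**The concern.** The size threshold equals the effect for which the trial was sized. The protocol's 80% was calculated for a significance test, and the SAP then changed what counts as success without restating the power. A reader sent from the SAP to the protocol is given 80% as the only power figure for the primary claims.

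The issue is practical. The SAP's account of the MID says that smaller HbA1c reductions were expected here than the 3 to 7 mmol/mol of earlier studies, so a true effect near 3.5 is a realistic case. If such an effect exists and the claim is missed, a reader who believes the trial had an 80% chance of making it may take the miss as evidence against an effect of the planned size.

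**Working it through.** **Inputs.** SD 7 mmol/mol, two-sided 5%, 64 evaluable per arm, difference 3.5 mmol/mol (Protocol 13.3). MAGE: 0.35 mmol/l, SD 0.7 (Protocol 13.3, Table 5). MID: 3.5 and 0.35 (SAP Section 6). Both endpoints have standardised effect 0.5, so the MAGE results are the HbA1c results divided by 10.

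**1. The protocol's figure.** SE = 7 × √(2/64) = 1.237 mmol/mol. Power by the normal approximation = Φ(3.5/1.237 − 1.960) = Φ(0.868) = 80.7%; by the noncentral t, 80.1%. By the t-test, 64 is the smallest number per arm that reaches 80%. The stated figure reproduces for the test alone.

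**2. Smallest significant estimate.** t(0.975; 126 df) × SE = 1.979 × 1.237 = 2.45 mmol/mol (0.245 mmol/l for MAGE). This is below the MID, so any estimate that reaches the MID is already significant. The size condition alone decides.

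**3. Chance of a claim under the two-part rule.** P(estimate ≥ 3.5) = 1 − Φ((3.5 − δ)/1.237) for a true difference δ. At δ = 3.5 this is 1 − Φ(0) = 50%.

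| True HbA1c difference (mmol/mol) | Two-part rule | Significance alone (normal) |
|---|---|---|
| 3.0 | 34% | 68% |
| 3.5 | 50% | 81% (80% by t) |
| 4.0 | 66% | 90% |

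**4. Significant but not claimable.** At δ = 3.5: 80.7% − 50.0% = 30.7%, per endpoint and comparison.

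**5. True difference needed for an 80% chance of a claim.** 3.5 + 0.842 × 1.237 = 4.54 mmol/mol (0.454 mmol/l). If all 77 per arm are analysed, SE = 7 × √(2/77) = 1.128 and the figure is 3.5 + 0.842 × 1.128 = 4.45 mmol/mol.

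**6. Sensitivity of the 50%.** It holds as long as the significance threshold lies below the MID, that is SE ≤ 3.5/1.96 = 1.786. With SD 7 this means at least 31 per arm, since 2 × (1.96 × 7/3.5)² = 30.7. With 64 per arm it means SD up to 1.786/√(2/64) = 10.1. Above that SD the significance condition binds and the chance is below 50%. A simulation with the SD estimated from the data (400,000 runs per scenario) gave 49.9% to 50.1% at 62, 64 and 77 per arm. Going from 64 to 77 per arm raises the power of the test alone from 80% to 87% and leaves the two-part rule at 50%.

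**7. Either endpoint sufficient.** The hypotheses are worded for HbA1c or MAGE. The documents give no correlation between the endpoints, so a range is assumed. If both true effects equal their MIDs, the chance of at least one claim is 1 − 0.5² = 75% at correlation 0, and 70%, 67% and 60% at 0.3, 0.5 and 0.8. Significance alone gives 96%, 94% and 92% at 0, 0.3 and 0.5. If only one endpoint has the planned effect and the other has none, the chance stays at 50%.

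**The case against.** The strongest reply is that neither document states anything false. The protocol ties its 80% to a two-sided 5% test, and the SAP sets out both conditions openly. A 50% chance at the threshold is inherent in any cut-off on a point estimate. The rule also has a benefit: with no true effect, P(estimate ≥ 3.5) = 1 − Φ(3.5/1.237) = 0.23% per test, against 2.5% for significance in the favourable direction. The SAP gives no other multiplicity control for its primary outcomes. Estimates and 95% CIs will be reported whatever the claim, and the sample size can no longer be changed.

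All of that stands, and it limits the seriousness of the point: no result is hidden and no bias is alleged. It does not make 80% the power of the rule that the SAP uses, and the SAP still takes its sample size justification from that figure.

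Three narrower replies:

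- Letting either endpoint suffice raises the chance to between 60% and 75%, and only if both effects are at their MIDs. That is still below 80%.
- The protocol's text attaches the MAGE power to 77 per group, where the test alone would have 87%. Table 5 shows that 77 is the enrolled number and 64 per arm the evaluable one, so 80% is right for that test.
- If MAGE is log-transformed, as SAP Section 6 permits, the result is a ratio and an absolute 0.35 mmol/l does not apply directly. This qualifies the MAGE figures and leaves HbA1c untouched unless HbA1c is itself transformed.

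**Conclusion.** The concern holds. At the planned effect the SAP's superiority rule succeeds 50% of the time per endpoint and comparison, against the 80% that the reader is referred to. An 80% chance of a claim needs a true difference about 30% larger than planned (4.54/3.5 = 1.30). The 50% rests on an approximately unbiased, symmetric estimate and on an SE no greater than 1.786 mmol/mol. It does not otherwise depend on the SD, on dropout, or on precision gained from the baseline-corrected model. The figures at other true effects, and the 4.54, do use SD 7 and 64 per arm. The point should be fixed: it concerns how the primary conclusion will be read, not the validity of the estimates.

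**What to change.** In SAP Section 3, replace the bare reference to the protocol with a statement such as:

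> The protocol's 80% power (64 evaluable per arm) applies to the two-sided 5% test alone. Under the two-part rule in Section 2, the chance of a superiority claim, per endpoint and comparison, is 50% at a true difference of 3.5 mmol/mol (HbA1c) or 0.35 mmol/l (MAGE). It reaches 80% only at about 4.5 mmol/mol or 0.45 mmol/l. The MAGE figures apply on the untransformed scale.

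It would help to add the false-claim rate (0.23% per test with no true effect) and the range for either endpoint (60% to 75%, with the assumed correlations), so that the rule is described from both sides.

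This costs a few sentences, needs no new data and leaves the decision rule as it is. There is time, since "The results will be analysed when this statistical analysis plan has been uploaded".

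Removing the size condition is not asked for. It would relax a success criterion after randomisation and measurement in an open-label trial, and four uncorrected primary tests would carry a family-wise error of about 16–17% two-sided (8–9% in the favourable direction). If the sponsor prefers to base the claim on the test and report the MID comparison separately, multiplicity control is needed. Holm at its strictest step (alpha 0.05/4 = 0.0125) gives 62% power at 3.5 mmol/mol, not 80%.
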